#### 11.3 Additional Safety Evaluations

#### **Physical Examination**

Physical examination at screening and end-of-trial will be listed for subjects with abnormal findings.

#### **Gynaecological Examination**

Gynaecological examination at screening and end-of-trial will be listed for subjects with abnormal findings.

## 12 INTERIM ANALYSES

No interim analysis is planned.

## **13 DEVIATIONS FROM THE PROTOCOL**

This SAP introduces the following changes to the analyses described in the trial protocol:

- A supplementary analysis of the primary efficacy endpoint using the PP analysis set (Section 10.1).
- Fertilisation rates (Section 10.2) and implantation rates (Section 10.4) will be estimated using negative binomial models with an offset to account for the differences in retrieved

oocytes and transferred blastocysts, respectively. This method was considered more appropriate than the mixed effects models described in the protocol as the proportion of subjects with a single observation is expected to be substantial.

• Exposure and treatment compliance (Section 9) will be tabulated for the Safety Analysis Set instead of the Full Analysis Set

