### 4 SELECTION OF TRIAL POPULATION

#### 4.1 Trial Population

#### 4.1.1 Inclusion Criteria

Subjects must meet all of the criteria listed below to be eligible for participation in the trial.

- 1. Informed Consent Form signed prior to screening evaluations.
- 2. In good physical and mental health.
- 3. Pre-menopausal females between the ages of 18 and 40 years. The subjects must be at least 18 years (including the 18th birthday) when they sign the informed consent and no more than 40 years (up to the day before the 41st birthday) at the time of randomisation.
- 4. Infertile women diagnosed with tubal infertility, unexplained infertility, endometriosis stage I/II or with partners diagnosed with male factor infertility, eligible for in vitro fertilisation (IVF) and/or intracytoplasmic sperm injection (ICSI) using fresh or frozen ejaculated sperm from male partner or sperm donor.
- Infertility for at least one year before randomisation for subjects ≤37 years or for at least 6 months for subjects ≥38 years (not applicable in case of tubal or severe male factor infertility).
- 6. Regular menstrual cycles of 21-35 days (both inclusive), presumed to be ovulatory.
- 7. Transvaginal ultrasound documenting presence and adequate visualisation of both ovaries, without evidence of significant abnormality (e.g. no endometrioma greater than 3 cm, and no enlarged ovaries or ovarian cyst not due to polycystic ovarian syndrome, which would contraindicate the use of gonadotropins) and normal adnexa (e.g. no hydrosalpinx) within 1 year prior to randomisation. Both ovaries must be accessible for oocyte retrieval.
- 8. Early follicular phase (cycle day 2-4) serum levels of FSH between 1 and 15 IU/L (results obtained within 3 months prior to randomisation).

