# Number of Fertilised Oocytes and Fertilisation Rate

An oocyte is defined as fertilised if it is scored as 2 pronuclei on day 1 after oocyte retrieval. The mean number of fertilised oocytes will be compared between treatments using the same analysis method as for the primary endpoint.

The proportion of oocytes becoming fertilised will be estimated and compared between treatments using a mixed effect binomial model with treatment and AMH level at stimulation day 1 (AMH <15 pmol/L, AMH  $\geq$ 15 pmol/L, or missing) as fixed factors, and subject as random factor, assuming normally distributed log-odds. The treatment difference in fertilisation probability and the associated 95% confidence interval will be derived using the delta method. This analysis is based on subjects with >0 oocytes retrieved only and is therefore not randomisation based. The fertilisation ratio is expected to be equal for the two treatments. If this is not the case, the reason for differences will be further explored by including e.g. number of oocytes retrieved as a covariate in the analysis model.

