#### **3.2** Determination of Sample Size

In a previous trial (MERIT), 347 subjects aged 22-37 years were treated with a starting dose of 225 IU GONAL-F. In these subjects the mean number of oocytes retrieved was 11.8 and the standard deviation was 5.7. Assuming that the standard deviation for number of oocytes retrieved in this trial will be 6.0, a total sample size of 300 with a 2:1 randomisation will give a 2-sided 95% confidence interval ranging from -1.44 to +1.44 oocytes from the observed difference. This level of precision is considered as sufficient and is also more precise than the equivalence limits of  $\pm 3$  oocytes that has been applied in previous trials comparing biosimilar FSH compounds.

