# Number of Fertilised Oocytes and Fertilisation Rate

An oocyte is defined as correctly fertilised if it is scored as 2 pronuclei (PN) on day 1 after oocyte retrieval. The mean number of correctly fertilised oocytes will be compared between treatments using the same analysis method as for the primary endpoint.

For subjects with >0 oocytes retrieved, the rate of correctly fertilised oocytes to oocytes retrieved will be estimated and compared between treatments using a negative binomial regression model with treatment and AMH level at stimulation day 1 (AMH <15 pmol/L, AMH  $\ge$ 15 pmol/L, or missing) as factors and the number of retrieved oocytes (log-transformed) as an offset. The treatment difference in fertilisation rate and the associated 95% confidence interval will be derived using the delta method.

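### SAP Section 13's reason for dropping the binomial model does not fit fertilisation rate, and the replacement count model can overstate the standard error when subjects vary little

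*Combined protocol and SAP*

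**What the plan says.** Protocol 7.2.3 defines fertilisation rate as 2PN oocytes over oocytes retrieved, so the numerator is bounded by the denominator. Protocol 9.7.3 compares the arms "using a mixed effect binomial model with treatment and AMH level at stimulation day 1", plus a random effect for subject, in subjects with at least one oocyte. It expects the two arms to be equal on this endpoint.

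SAP 10.2 keeps the same subjects but fits a negative binomial regression with treatment and AMH category "as factors and the number of retrieved oocytes (log-transformed) as an offset". The difference in rates and its 95% interval come from the delta method, and Table 10-1 lists the endpoint under negative binomial regression. SAP Section 13 discloses the change together with the one for implantation rate, and gives a single reason for both: "the proportion of subjects with a single observation is expected to be substantial".

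**The concern.** Within a subject, the units for fertilisation are oocytes. The trial plans on about 12 per subject, so a reason based on subjects with one unit looks borrowed from implantation, where the units are transferred blastocysts and may often number one.

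The replacement also treats a bounded count as unbounded. A negative binomial count has variance of at least its mean, whereas a binomial count has less. If subjects differ little in fertilisation probability, the model cannot reach the true, smaller variance and the interval comes out too wide. An inflated interval could mask a departure from the equality that the protocol expects.

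**Working it through.** **Inputs from the documents.** On the earlier trial, SAP 3.2 states: "In these subjects the mean number of oocytes retrieved was 11.8 and the standard deviation was 5.7". It assumes that "the standard deviation for number of oocytes retrieved in this trial will be 6.0", and that "a total sample size of 300 with a 2:1 randomisation will give a 2-sided 95% confidence interval ranging from -1.44 to +1.44 oocytes". The documents give no fertilisation rate, no between-subject variation and no expected share of single-oocyte subjects. Fertilisation rates p of 50, 60 and 70% and the within-subject correlation ρ below are therefore assumptions.

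**Step 1. The plan's own figure.** 1.96 × 6.0 × √(1/200 + 1/100) = 1.44. It reproduces.

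**Step 2. Share of subjects with one oocyte.** Take a negative binomial with mean m and SD s: k = m²/(s² − m), P0 = (k/(k+m))^k, P1 = k × m/(k+m) × P0, share = P1/(1 − P0).

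- m = 11.8, s = 5.7: k = 139.24/20.69 = 6.73, P0 = 0.0011, P1 = 0.0047, share 0.47% (1.4 of 300).
- m = 11.8, s = 6.0: k = 139.24/24.2 = 5.75, P0 = 0.0016, P1 = 0.0063, share 0.63% (1.9 of 300).
- A rounded normal instead of a negative binomial gives 1.2-1.4%.

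The planning data come from younger women ("347 subjects aged 22-37 years were treated with a starting dose of 225 IU GONAL-F") than this trial admits ("Pre-menopausal females between the ages of 18 and 40 years"), so the mean may be lower. With s = 6.0, an assumed mean of 10 gives 2.0% and an assumed mean of 8 gives 5.9%.

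**Step 3. Variance floor.** Given n oocytes, the negative binomial variance is np + α(np)², which is at least np. The variance of a bounded count with correlation ρ is np(1 − p)[1 + (n − 1)ρ]. When α sits at its lower bound, the ratio of model to true standard error is about 1/√{(1 − p)[1 + (ñ − 1)ρ]}. Here ñ is the size-weighted mean count, m + s²/m = 11.8 + 32.49/11.8 = 14.55.

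| ρ | p = 0.5 | p = 0.6 | p = 0.7 |
|---|---|---|---|
| 0 | 1.41 | 1.58 | 1.83 |
| 0.05 | 1.09 | 1.22 | 1.41 |
| 0.1 | floor no longer binds | 1.03 | 1.19 |

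Example at p = 0.6, ρ = 0.05, taking all 300 subjects to have oocytes. The count model's half-width is 1.96 × √(0.6/11.8) × √(1/200 + 1/100) = 0.054, or ±5.4 percentage points. A correct binomial analysis gives 5.4/1.22 = ±4.4.

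**Step 4. Simulation.** 200 against 100 subjects, SAP model with treatment and a binary AMH factor. Cells are model SE over empirical SE at p = 0.5 / 0.6 / 0.7.

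| ρ | Beta-binomial data, SD 5.7, 600 trials | Logistic-normal data, SD 6.0, 200 trials |
|---|---|---|
| 0 | 1.40 / 1.50 / 1.76 | 1.39 / 1.50 / 1.79 |
| 0.05 | 1.10 / 1.22 / 1.40 | 1.03 / 1.15 / 1.37 |
| 0.1 (right: 0.11-0.12) | 1.01 / 0.99 / 1.24 | 1.08 / 1.07 / 1.16 |
| 0.2 (right: 0.16-0.17) | 1.07 / 1.02 / 1.07 | 1.16 / 1.09 / 0.96 |
| 0.3 (right: 0.27-0.29) | 1.14 / 1.12 / 1.04 | 1.07 / 1.16 / 1.12 |

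A further simulation gave 1.3-1.85 at ρ = 0, 1.05-1.35 at 0.05 and 1.01-1.12 at 0.1-0.2. In the logistic-normal runs, coverage at ρ = 0 was 99.5-100%. The lowest ratio, 0.96, is within simulation error: the relative error of an empirical SE from 200 trials is about 1/√400 = 5%.

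**The case against.** A reader might infer that the SAP's interval will be much too wide. The documents do not support that, because the size turns on two quantities they omit. In the beta-binomial simulation, 9 of 15 scenarios have a ratio of 0.99-1.14. Zero correlation is a limiting case: the protocol's own model presumes that subjects differ, and the trial mixes infertility diagnoses and allows both IVF and ICSI. This objection stands, so the size can only be given as a conditional range.

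A reader might also infer that restoring the protocol's model as written settles the matter. It need not narrow the interval. At between-subject log-odds SDs of 0.8 and 1.0 and p of 0.5-0.6, the negative binomial interval was 0.88-0.93 times the width of the mixed model's. Part of that gap is a difference in target: a logistic-normal model gives a subject-specific probability unless averaged over the random effect, whereas protocol 7.2.3 defines a population rate. The mixed model's own SE ratios ran from 0.91 to 1.01 over 300 trials per scenario, so it is not beyond criticism. This also stands, and it changes the order of the remedies.

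The change is openly disclosed, SAP Section 1 lets the SAP supersede the protocol, and no margin or decision rule rests on this endpoint. That limits the consequence but does not supply a reason for the change. Nor does reading an observation as one aggregate record per subject: every subject would then have exactly one.

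**Conclusion.** The stated reason fails for fertilisation rate. About 0.5-0.6% of subjects with oocytes are expected to have exactly one, from the planning mean and SD and a negative binomial shape. The figures of about 2% and 6% at means of 10 and 8 are assumptions, and even these are not a substantial share. The criticism does not extend to implantation, where single-blastocyst transfer may be common.

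The replacement model has a structural weakness of conditional size. For assumed fertilisation rates of 50-70%, its standard error is about 1.3-1.85 times too large at correlation 0, about 1.05-1.4 times at 0.05, and roughly correct (up to about 1.25 times) at 0.1 or more. No scenario showed it clearly too small, so where the error occurs it is conservative. The endpoint is secondary, the SAP calls all analyses descriptive, and the primary analysis is untouched.

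**What to change.** In SAP 10.2, Table 10-1 and Section 13, analyse fertilisation rate as 2PN out of oocytes retrieved with a binomial-type model containing treatment and AMH category. Preferred options are a binomial model with subject-level robust variance or a beta-binomial model, since both estimate the population rate defined in protocol 7.2.3. The protocol's mixed binomial model is also acceptable if its probabilities are averaged over the random effect before the difference is taken. In Section 13, limit the single-observation reason to implantation rate.

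The cost is SAP wording and minor extra modelling work. No new data are needed.
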